5.5.1. Immunogenicity Data

The following immunogenicity assessments (assays) may be used in this study:

- The MSD-ECL Multiplex Assay (MSD-ECL = meso scale discovery – electrochemiluminescence assay) measures binding antibody to antigens corresponding to: Spike; the Receptor Binding Domain (RBD) of the Spike protein; and nucleocapsid protein, which is not contained in mRNA-1273.
- Pseudovirus nAb assay (PsVNA) for measuring neutralizing antibodies against SARS-CoV-2 Spike-pseudotyped viruses. Please see Appendix H for description of the pseudovirus nAb assay.

With the emergence of variants, neutralizing and/or binding antibodies against specific variants are of interest, and such data will be summarized and analyzed in the same way for that against the prototype strain.

5.5.2. Summary of Antibody-Mediated Immunogenicity Endpoints

Quantitative binding and neutralizing antibodies will be summarized by treatment group and by corresponding “baseline” SARS-CoV-2 status (e.g. baseline/pre-Day1, or pre-booster) if applicable:

- Geometric mean titer (GMT) or value with corresponding 95% CI will be provided at each time point. The 95% CIs will be calculated based on the t-distribution of the log-transformed values then back transformed to the original scale for presentation. The detail of calculation is provided in Appendix G.
- Geometric mean fold rise (GMFR) of titer with corresponding 95% CI will be provided at each post-baseline timepoint over corresponding baseline or reference at Day 1. GMFR may be calculated based on two types of baseline:
 - 1) pre-Dose 1 baseline prior to the first dose of mRNA-1273
 - 2) pre-booster baseline (where applicable)

The 95% CIs will be calculated based on the t-distribution of the log-transformed values then back transformed to the original scale for presentation. GMFR calculated from the pre-vaccination (pre-Dose 1) will be considered as the primary approach.

- Seropositivity rate (SRR), defined as proportion of subjects achieving seropositivity, will be provided with 2-sided 95% Clopper-Pearson CIs.

5.5.2.1.1. Seropositivity Rate (SRR) of the Primary Series and Booster

For each of the antibodies of interest, seropositivity rate (SRR) is defined as the proportion of participants achieving seropositivity.

Seropositivity of the booster is assessed based on two types of baselines (Pre-vaccination /Pre-Dose 1 of the primary series; Pre-booster) as described below. Seropositivity of a booster based on pre-vaccination (pre-Dose 1 of the primary series) value will be considered the primary definition of seropositivity of the booster:

- a 4-fold rise definition compared to Pre-vaccination (Pre-Dose 1 of the primary series) baseline, defined as
 - ≥ 4 -foldrise for those with Pre-vaccination /Pre-Dose 1 value \geq LLOQ
 - ≥ 4 *LLOQ for those with Pre-vaccination /Pre-Dose 1 value $<$ LLOQ;
 - If there is no pre-Dose 1 antibody titer information and there was evidence that the participant did not have SARS-CoV-2 infection prior to vaccination, i.e. negative SARS-CoV-2 status at the pre-vaccination/pre-dose 1 of primary series, these participants' pre-vaccination/pre-dose 1 antibody titer may be assumed to be $<$ LLOQ at pre-dose 1 of primary series.
- a 4-fold rise definition compared to Pre-booster value, defined as
 - ≥ 4 -foldrise for those with Pre-booster value \geq LLOQ
 - ≥ 4 *LLOQ for those with Pre-booster value $<$ LLOQ;

If an assay-specific definition proposed by the Sponsor is available, assay-specific SRR definitions based on the two types of baselines may be provided. Please refer to Appendix I on assay-specific definitions used for Part A analysis of immune response.

In addition to GMT, GMFR, SRR, the number and percentage of subjects with fold-rise ≥ 2 , and fold-rise ≥ 4 from baseline at each post injection time points will be tabulated with 2-sided 95% Clopper Pearson CI. For select nAb and bAb specific to S-protein, number and percentage of subjects with ≥ 4 *LLOQ at select timepoints with 2-sided 95% Clopper Pearson CI may also be provided.

For select nAb and bAb specific to S-protein, boxplots of antibodies, and reverse cumulative distribution function curve (RCDF) at timepoint of interest will be provided.

5.5.3. Analysis of Antibody-Mediated Immunogenicity Endpoints

5.5.3.1. Durability of immune response to the Primary Series: Mixed Model for Repeated Measures (MMRM)

At the completion of P301, if immunogenicity data of the primary series beyond Day 57 are deemed to be sufficient, an exploratory analysis using a mixed model for repeated measures (MMRM) may be carried out to characterize the immune response of the primary series of mRNA-1273 in SARS-CoV-2-specific nAb and S protein-specific bAb. The model may be carried out using SAS PROC MIXED. If performed, this analysis will be based on the participants on mRNA-1273 in the Part C PPIS-Neg (PPIS with negative pre-booster SARS-CoV-2 status).

For each select SARS-CoV-2-specific nAb and S protein-specific bAb of interest, the model will include all available log-transformed antibody titers at each post-Dose 1 of mRNA-1273 timepoints as the dependent variable. No treatment group variable in the model as all subjects in the model have received primary series of mRNA-1273. Visits will be re-parameterized with respect to target days post-Dose of the primary series of mRNA-1273. The model will include Visit (as a class variable) as fixed effects, with adjustment for stratification factor used for randomization, and subject as a random effect. The model may also adjust for other characteristics such as Sex. An unstructured covariance structure will be used to model the within-subject errors. A Kenward-Roger approximation will be used for the denominator degrees of freedom. If there is a convergence issue due to the unstructured covariance matrix, a compound symmetry covariance structure will be used to model the within-subject errors. No imputation of missing data will be done.

GMT at each post-Dose 1 of primary series timepoint will be estimated by the geometric least squares mean (GLSM) and corresponding 2-sided 95% CI estimated from the model. Ratio of GMT (change) between two timepoints may also be estimated by the ratio of GLSM. The corresponding 95% CI results in log-transformed scale estimated from the model will be back-transformed to obtain these estimates in the original scale.

5.5.3.2. Immunobridging of response of a Booster as compared to Primary Series

Immunobridging analyses of a booster as compared to the primary series will be performed using the neutralizing antibody titers (as measured by PsVNA) 28 days following the booster dose (BD-D29) to the corresponding titers 28 days following the second dose of the primary series (Day 57 of the blinded phase for the mRNA-1273 cohort).

Immunobridging analyses may also be performed using binding antibody specific to S-protein by MSD.

The following endpoints will be used for this analysis:

- Geometric mean titer (GMT)
- Seroreponse Rate (SRR)

For GMT:

In the situation that subjects in PPIS-Neg Set have the same specific nAb (e.g. PsVNA) at baseline/pre-Dose 1, 28 days after Dose 2 of primary series, pre-booster, 28 days after booster and other timepoints, GMT ratios will be calculated by back transforming the mean of within-subject paired differences of antibody titers on the logarithmic scale between post-booster Day 29 (of the booster phase) and Day 57 of primary series (Day 57 of the blinded phase for the mRNA-1273 cohort). CIs for the GMT ratio will be based on t-distribution of the log-transformed values then back transformed to the original scale for presentation.

Another approach is to compare the post-booster antibody titers in Part C with the post-primary series titers in baseline-SARS-CoV-2 negative mRNA-1273 participants. An analysis of covariance (ANCOVA) model will be performed using the Part C PPIS-Neg Set with baseline-SARS-CoV-2 negative mRNA-1273 participants in PPSI (considering as historical control). In the model, antibody titers at 28 days post-booster (BD-Day 29) and post-Dose 2 of primary series will be a dependent variable, and a group variable (Booster and mRNA-1273 primary series) will be the fixed effect, adjusting for age groups (< 65, ≥ 65 years). The GMT will be estimated by the geometric least square mean (GLSM) from the model and its corresponding 95% CI will be provided for each group. The GMR (ratio of GMTs) for Booster with respect to mRNA-1273 primary series will be estimated by the ratio of GLSM from the model and the corresponding 95% CI will be provided. The 95% CI for

GMR will be used to assess the between group difference in immune response 28 days post-booster as compared to 28 days post-Dose 2 of the primary series.

For Seroresponse:

Seroresponse of a booster will be compared with that of the primary series based on the of the SRR difference (booster – the primary series) and seroresponse based on change (fold rise) from pre-vaccination (pre-dose 1 of the primary series) would be considered the primary approach.

Using Part C PPIS-Neg, SRR at Day 29 of the booster phase will be compared with the SRR at Day 57 of primary series (Day 57 of the blinded phase for the mRNA-1273 cohort or OL-D57 for the Placebo-mRNA-1273 cohort). The difference in SRR and its corresponding 95% CI based on adjusted Wald method (Bonett et al 2012) will be provided. If feasible, the adjusted Wald method is adopted owing to the fact that the seroresponses at different time points can be paired within each participant.

If within-subject paired-comparison is not feasible, the Miettinen-Nurminen’s method will be used to calculate the 95% CI for SRR difference (booster – primary series). Baseline-SARS-CoV-2 negative mRNA-1273 participants in PPRSI, as historical control, will be compared with PPIS-Neg regarding SRR difference (booster – primary series).

The 95% confidence interval (CI) of the ratio of GMT ratio (GMR) and 95% CI of seroresponse rate (SRR) difference will be used to assess the immune response of a booster (50 µg mRNA-1273) as compared to mRNA-1273 100 µg Primary Series (PS). All tests will be performed at nominal alpha level of 0.05 (2-sided). The table below lists possible scenarios of GMR and SRR difference results and corresponding conclusions.

Endpoints	Scenario		Conclusion
GMT Ratio	1	Lower bound of 95% CI of GMR ($GMT_{\text{booster}} / GMT_{\text{mRNA-1273 PS}} < 0.67$)	Non-inferiority of a booster as compared to mRNA-1273 100 µg primary series (PS) based on GMR is not demonstrated

	2	$0.67 \leq$ Lower bound of 95% CI of GMR ($\text{GMT}_{\text{booster}} / \text{GMT}_{\text{mRNA-1273 PS}} \leq 1$)	Non-inferior of a booster as compared to mRNA-1273 PS based on GMR is demonstrated but superiority is not demonstrated
	3	Lower bound of 95% CI of GMR ($\text{GMT}_{\text{booster}} / \text{GMT}_{\text{mRNA-1273 PS}} > 1$)	Superiority of a booster as compared to mRNA-1273 PS based on GMR is demonstrated
SRR Difference	1	Lower bound of 95% CI of SRR difference ($\text{SRR}_{\text{booster}} - \text{SRR}_{\text{mRNA-1273 PS}} \leq -10\%$)	Non-inferiority of a booster as compared to mRNA-1273 PS based on SRR difference is not demonstrated
	2	$-10\% <$ Lower bound of 95% CI of SRR difference ($\text{SRR}_{\text{booster}} - \text{SRR}_{\text{mRNA-1273 PS}} \leq 0$)	Non-inferiority of a booster as compared to mRNA-1273 PS based on SRR difference is demonstrated but superiority is not demonstrated
	3	Lower bound of 95% CI of SRR difference ($\text{SRR}_{\text{booster}} - \text{SRR}_{\text{mRNA-1273 PS}} > 0$)	Superiority of a booster as compared to mRNA-1273 PS based on SRR difference is demonstrated

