6.7.1. Sampling of the Immunogenicity Subset (Case-cohort Sampling Design)

For characterizing immunogenicity of the vaccine, and for assessing correlates of risk and protection (CoR/CoP), a case-cohort sampling design will be used for measuring bAb and nAb data from a randomly sampled subset of trial participants [the case-cohort Immunogenicity Analysis Set (ccIAS)], or Immunogenicity Subset. The ccIAS cohort consists of a stratified random sample of trial participants (Random SubCohort), augmented with a subset of all primary endpoint cases and SARS-CoV-2 infection endpoint cases. The immunogenicity samples of the ccIAS cohort will be processed and the immunogenicity data will be available for the ccIAS cohort.

A case-cohort sampling design (Prentice (1986)) is used for measuring antibody markers in a random sample of study participants and from all or a subset of cases of COVID-19 primary endpoint (COV-DIS) and infection endpoint (COV-INF) (Figure 3). The random sample is stratified by the key baseline characteristics: assigned treatment arm, baseline SARS-CoV-2 status (defined in Section 6.1), stratification factor used for randomization, and minority (defined as Race being Blacks or African Americans, American Indians or Alaska Natives, Native Hawaiians, and other Pacific Islanders; or Ethnicity being Hispanics or Latinos).

This design uses a stratified random sample instead of the simple random sample proposed by Prentice (1986), the design may also be referred to as a two-phase sampling design, where “phase one” refers to variables measured in all participants and “phase two” refers to variables only measured in a subset (thus the “case-cohort sample” constitutes the phase-two data, e.g. antibodies).

Figure 3: Case-cohort sampling design: participants selected into the stratified random sample (Random Subcohort) and in all or a subset of COVID-19 and COV-INF cases occurring outside of the Random Subcohort.

The Immunogenicity Subset will be used to characterize immunogenicity of mRNA-1273, and to assess correlates of risk and protection. The analysis of characterizing immunogenicity of mRNA-1273 is included in Section 6.7 of this SAP; the analysis of assessing correlates of risk and protection will be included in a separate Immune Correlates SAP.

Eligibility criteria for Immunogenicity SubSet

For stratified random sample:

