In addition, an analysis of covariance (ANCOVA) model with the treatment group as explanatory variables, adjusting for the stratification factor at randomization, baseline value if applicable, will be used to assess the treatment effect at specific timepoints (scheduled visits) such as Day 57. GLSM with 95% CI for each treatment group, GMR with 95% CI for treatment difference will be estimated from the ANCOVA model. The model may also adjust for minority group used to sample for the random subcohort.

6.7.6. Summary of Immunogenicity in COVID-19 Cases on mRNA-1273 with negative SARS-CoV-2 status at baseline

To characterize immunogenicity of mRNA-1273, immunogenicity data (Section 6.7.3) will be analyzed using the Per-Protocol Random Subcohort for Immunogenicity.

It is of interest to examine the immune response in subjects on mRNA-1273 with baseline SARS-CoV-2 negative status who were COVID-19 or SARS-CoV-2 infection cases. Summary of immunogenicity may be provided in a subset of baseline SARS-CoV-2 negative participants on mRNA-1273 who were COVID-19 cases based on adjudication committee assessments.

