5.5. Immunogenicity Analysis

The secondary immunogenicity objective (Part A), to evaluate the immunogenicity of 2 doses of mRNA-1273 given 28 days apart, have been evaluated and summarized in the Part A CSR (dated 03 Aug 2021) using the Per-protocol stratified random subcohort (PPRSI). mRNA-1273 was highly immunogenic as measured by both bAb and nAb in both SARS-CoV-2 baseline-negative and baseline-positive individuals, as indicated by increased bAb and nAb levels 1 month after first injection (Day 29) and 1 month after second injection (Day 57).

This SAP includes analyses of immunogenicity data to evaluate the immunogenicity of mRNA-1273 primary series and booster.

In principle, summary (descriptive statistics) will be provided for available immunogenicity data by timepoints in relative of primary series and booster dose respectively. Comparison or analysis to assess difference between groups (Section 5.5.3) will only be performed using the same assay from the same (central) testing lab.

For immune response to a booster, Part C PPIS (Part C Per-Protocol Immunogenicity Subset), defined in Section 4.3, will be used for summaries of immune response, and data will be presented by pre-booster SARS-CoV-2 status. Part C PPIS-Neg, Part C PPIS – Pre-booster SARS-CoV-2 Negative defined in Section 4.4, will be used as the primary analysis population for comparison of immune response, either as paired-comparison when a subject serves as his/her own control; or between-group comparison compared to post-primary series in Part A using mRNA-1273 subjects in PPRSI with negative baseline SARS-CoV-2 as historical control.

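### The historical-control ANCOVA for the Part C booster GMR adjusts for age group only; adding the risk and minority strata, and a rule that the paired GMR decides, would be a near-free improvement

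*SAP*

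**What the plan says.** SAP Part B/C 5.5.3.2 compares titers at BD-Day 29 with titers at Day 57 of the primary series.

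- **Paired route, listed first.** If participants have the same assay at the listed timepoints, "GMT ratios will be calculated by back transforming the mean of within-subject paired differences of antibody titers on the logarithmic scale".
- **ANCOVA route.** "Another approach is to compare the post-booster antibody titers in Part C with the post-primary series titers". The booster group is Part C PPIS-Neg. The comparator is the baseline-negative mRNA-1273 participants of the Part A random subcohort ("considering as historical control"). The group variable "will be the fixed effect, adjusting for age groups", cut at 65 years, and no other covariate is named.

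Section 5.5 presents these as alternatives, "either as paired-comparison when a subject serves as his/her own control" being the first. For seroresponse, 5.5.3.2 says that the unpaired method is used when pairing is not feasible. For GMT it does not say which result decides if both can be computed. Protocol 9.5.3.2 names only a t-based interval for the mean log difference.

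The subcohort was stratified by arm, baseline SARS-CoV-2 status, "stratification factor used for randomization, and minority" (SAP Part A 6.7.1). The Part A models adjust for the randomisation stratification factor, and of minority status SAP Part A 6.7.5 says "The model may also adjust for minority group used to sample for the random subcohort". The MMRM in SAP Part B/C 5.5.3.1 also adjusts for the stratification factor.

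**The concern.** PPIS-Neg is the part of the subcohort that received a booster and had no evidence of infection before it (SAP Part B/C 4.3 and 4.4). Both conditions arise after randomisation, and taking a booster is the participant's choice (protocol 4.1.3). Nothing keeps the mix of at-risk and minority participants equal to that of the control. In its booster effectiveness analysis (5.6.2.2) the same SAP warns of confounding by who chooses a booster early or late, and it lists race/ethnicity among further covariates to examine.

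The non-randomised GMR model therefore has a narrower covariate set than the SAPs' other titer models, and no reason is given. The lower confidence limit of the GMR is read against 0.67 for non-inferiority and against 1 for superiority, so a shift of a few percent matters if the limit falls near either value. Variation that known strata could explain also stays in the residual and widens the interval.

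**Working it through.** **The plan's own figures.** SAP Part A Table 6 plans 150 evaluable baseline-negative mRNA-1273 participants in each of six strata (three age/risk groups by minority status), so 6 × 150 = 900. Over all strata, 900 + 120 + 600 = 1,620 evaluable. Allowing for 15% exclusion, 1,620 / 0.85 = 1,906, against 1,944 stated (2.0% apart). The margin is 1/1.5 = 0.667. No titer SD, stratum GMT, booster uptake by stratum or Part C sample size is given.

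**When bias arises.** Both ANCOVA groups come from the same stratified subcohort, so stratified sampling alone creates no imbalance. Bias needs two things together: entry to PPIS-Neg differs by stratum, and titers differ by stratum. For one binary characteristic, balanced over age,

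bias factor = r^d,

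where r is the GMT ratio between categories and d is the difference in their share between groups.

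**Base range (assumed r and d).**
- r = 0.8, d = 0.20: 0.8^0.2 = 0.956
- r = 0.85, d = 0.20: 0.85^0.2 = 0.968
- r = 0.9, d = 0.10: 0.9^0.1 = 0.990

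If the direction is reversed, the factors invert: 1/0.956 = 1.046 and 1/0.990 = 1.010.

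**Wider stress test (all inputs assumed).** True GMR 1.00, control of 150 per stratum, age-only model. Uptake is given as non-minority/minority, and the minority share is 50% in the control. Each range runs from a stratum GMT ratio of 1.1 to one of 2.0.

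| Uptake | Minority share in booster group | Minority only | Risk also differs, same direction |
|---|---|---|---|
| 70% / 50% | 0.5/1.2 = 0.417 | 0.992 to 0.944 | 0.987 to 0.909 |
| 75% / 40% | 0.4/1.15 = 0.348 | 0.986 to 0.900 | 0.977 to 0.842 |
| 80% / 30% | 0.3/1.1 = 0.273 | 0.979 to 0.854 | 0.966 to 0.776 |

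As a check on the first row, d = 0.5 − 0.417 = 0.083 and 2.0^(−0.083) = 0.944. With all six strata in the model the result is 1.000 in every cell. With equal uptake it is 1.000 even with age only.

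**Adding the paired estimator.** A simulation of 400 runs per case (assumed log-titer SD 1.0, within-person correlation 0.5) gave these mean GMRs for paired / age-only / six-strata:
- 70%/50%, ratio 1.25: 0.996 / 0.977 / 0.995
- 75%/40%, ratio 1.5: 1.001 / 0.942 / 1.002
- 80%/30%, ratio 2.0: 1.002 / 0.858 / 1.004

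The paired and six-strata estimates stay at about 1.00. Only the age-only model moves.

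**The case against.** The strongest reply is that the plan already contains an analysis free of this problem, and lists it first. In the paired route each participant is their own control, so stratum mix cannot differ. Pairing should usually be possible, because PPIS-Neg lies within the per-protocol subcohort and subcohort members needed Day 1 and Day 57 serum (SAP Part A 6.7.1). The rule in SAP Part B/C 5.5 that comparisons use one assay and one laboratory binds the ANCOVA equally. This stands, and it limits the point to the second route. It does not remove the point. The paired route is conditional, its condition lists more timepoints than the difference needs, and no rule makes the ANCOVA a fallback for GMT.

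A second reply is that the effect is immaterial. Protocol 2.2.2 and 4.3 report that a 50 µg booster in Study 201 reached 1.7-fold the primary-series peak of this trial. If that held here, 1.7 × 0.956 = 1.63, and even the most extreme stress-test factor gives 1.7 × 0.776 = 1.32. This also stands as an expectation, though not as a reason to leave out recorded covariates.

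A third reply is that Part A makes minority adjustment optional, so six full strata go a step beyond Part A practice. That is true, but the Part A comparison was randomised and this one is not.

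**Conclusion.** The point holds as a minor improvement to the ANCOVA route. Its covariate set is narrower than that of the SAPs' other titer models, in the comparison that most needs adjustment. Under the base assumptions the factor is about 0.96 to 0.99, or its inverse. Neither its size nor its direction can be derived from the documents.

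A reader might infer that the Part C GMR is biased whichever route is used, that stratified sampling itself unbalances the groups, or that the non-inferiority conclusion is at risk. The documents support none of these. The paired GMR is unaffected by composition, both groups share one sampling frame, and no assumed case takes a true GMR of 1.00 below 0.67. What remains is a possible shift in a lower limit that already lies near 0.67 or 1.

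Stratum adjustment has limits too. It does not remove selection on titer itself, such as the exclusion of participants infected before the booster. It also does not deal with the same people entering both ANCOVA groups: the control as described contains the booster group, and no handling of that correlation is stated.

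**What to change.** In SAP Part B/C 5.5.3.2:

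1. Replace the age-group term in the ANCOVA with the randomisation stratification factor and minority status, as the six sampling strata of SAP Part A Table 6. Report the age-only model as a sensitivity analysis.
2. State for GMT, as is done for seroresponse, that the paired GMR decides when feasible and that the ANCOVA is used only otherwise. Define feasible as a Day 57 and BD-Day 29 result from the same assay and laboratory.
3. If the ANCOVA is kept, say how participants who appear in both groups are handled, and correct the control set's label: PPSI is not defined, and section 5.5 uses PPRSI.

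The cost is SAP wording. Six strata use five degrees of freedom instead of one, so four more. The covariates had to be non-missing for sampling (SAP Part A 6.7.1), so no new data are needed.

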9.5. Statistical Analyses

This section provides a summary of the planned statistical analyses of the primary and secondary endpoints.

The overall Type I error rate for the primary endpoint at the IAs and the primary analysis is strictly controlled at 2.5% (1-sided) based on the Lan-DeMets O'Brien-Fleming approximation spending function (see [Section 9.6](#) for details). The primary efficacy results that will be considered statistically significant after consideration of the strategy for controlling the Type I error as described in [Section 9.6](#). Statistical significance of the primary efficacy endpoint can be achieved at either one of the IAs or at the primary analysis. A sequential/hierarchical testing procedure will be used to control Type 1 error rate over the primary efficacy endpoint and the secondary efficacy endpoints. Secondary efficacy endpoints will only be tested when the primary efficacy endpoint achieves statistical significance. Multiplicity adjustments among the secondary efficacy endpoints may be performed for secondary efficacy endpoints, in that case, will be specified in the SAP.

No formal multiple comparison adjustments will be employed for multiple safety endpoints or multiple efficacy endpoints. Nominal p-values and CIs may be computed for other efficacy analyses without controlling for multiplicity as a measure of VE.

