9.5.3.2. Part C

In Part C, the immunogenicity analysis of BD vaccine response will be performed using the noninferiority tests of the 2 null hypotheses based on the 2 key secondary endpoints, respectively. Further considerations for immunogenicity analyses are provided in the SAP.

Part C Key Secondary Endpoint 1: Ab GMT at BD-Day 29

Hypothesis: immunogenicity response to mRNA-1273 BD as measured by Ab GMT at BD-Day 29 in Part C is noninferior compared with Ab GMT at Day 57 (28 days after second dose) in the primary series of mRNA-1273.

The noninferiority of post-booster GMT at BD-Day 29 in Part C as compared to the primary series at Day 57 is considered to be demonstrated if the lower bound of the 95% CI of the GMR (ratio of GMT at BD-Day 29 vs. GMT at Day 57 [28 days after Dose 2 of the primary series]) is ≥ 0.67 using a noninferiority margin of 1.5 (1.5-fold immuno-bridging margin for the lower bound of the 95% CI for GMT ratio/GMR).

The GMT with 95% CI will be summarized using t-distribution of the log transferred values and then back transformed to the original scale. The GMR with 95% CI to compare post-booster GMT at BD-Day 29 in Part C with the primary series GMT at Day 57 (28 days after the second dose) will be computed based on the t-distribution of mean difference in the log transferred values and then back transformed to the original scale.

Part C Key Secondary Endpoint 2: Ab Seroresponse Rate at BD-Day 29

Hypothesis: immunogenicity response to mRNA-1273 BD as measured by seroresponse rate (SRR) at BD-Day 29 in Part C is noninferior compared with SRR of the primary series at Day 57 (28 days after second dose of the primary series of mRNA-1273).

The noninferiority in SRR post-booster at BD-Day 29 in Part C compared with SRR of the primary series at Day 57 (28 days after the second dose of the primary series of mRNA-1273) is considered to be demonstrated if the lower bound of the 95% CI of the SRR difference (SRR of the booster at BD-Day 29 – SRR of the primary series at Day 57) is $> -10\%$ (using the noninferiority margin of 10%). The SRR difference is defined as the seroresponse rate at BD-Day 29 in Part C minus the seroresponse rate at Day 57 (28 days after the second dose) following the primary series of mRNA-1273. The seroresponse of a booster or the primary series is defined as a titer change from baseline (pre-Dose 1 in primary series) below the LLOQ to $\geq 4 \times$ LLOQ, or at least a 4-fold rise if baseline is \geq LLOQ.

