The SRR with 95% CI (using Clopper-Pearson method) will be provided. The SRR difference with 95% CI to compare post-booster SRR at BD-Day 29 in Part C with the primary series SRR at

Day 57 (28 days after the second dose) will be computed. The method for computing 95% CI of seroresponse rate difference will be provided in the SAP.

The primary immunogenicity objective in Part C is met if noninferiority is demonstrated based on both key secondary endpoints (both GMT and SRR) .

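### The Part C SAP adds unplanned, unordered superiority conclusions for GMT and seroresponse, so the chance of at least one false superiority conclusion can exceed 2.5% (at most 5% per assay)

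*SAP*

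**What the plan says.** Protocol 9.5.3.2 defines two Part C comparisons of BD-Day 29 with Day 57 of the primary series, both for noninferiority:

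- GMT: the lower 95% limit of the GMR must be at least "0.67 using a noninferiority margin of 1.5".
- SRR: the lower 95% limit of the difference must be above -10% ("using the noninferiority margin of 10" percent).

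The success rule joins them: "The primary immunogenicity objective in Part C is met if noninferiority is demonstrated based on both key secondary endpoints". No superiority hypothesis appears there or in Protocol 9.2, which refers to that section for immunogenicity testing. On multiplicity, Protocol 9.5 states: "No formal multiple comparison adjustments will be employed for multiple safety endpoints or multiple efficacy endpoints". That sentence does not name immunogenicity.

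The SAP for Parts B and C, 5.5.3.2, sets the level ("All tests will be performed at nominal alpha level of 0.05 (2-sided") and gives a three-row decision table for each endpoint. Row 3 applies when the lower limit of the GMR exceeds 1 ("Superiority of a booster as compared to mRNA-1273 PS based on GMR is demonstrated") or when the lower limit of the SRR difference exceeds 0 ("Superiority of a booster as compared to mRNA-1273 PS based on SRR difference is demonstrated"). Neither table refers to the other endpoint. The section states no order, no alpha split and no exploratory status. It also allows the same analysis on MSD binding antibody in addition to the pseudovirus neutralization assay (PsVNA). Section 6 of that SAP lists no departures from the protocol.

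**The concern.** Two noninferiority tests that must both pass need no alpha adjustment. Moving from noninferiority to superiority on the same endpoint, using the same interval, costs nothing either. The table goes further: it offers two separate routes to a formal superiority statement, each at the full level. If the booster is no better than the primary series on either measure, there are two chances to say otherwise, and nothing in the section limits the combined chance.

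At stake is how a superiority statement may be read. The wording is that of a confirmatory conclusion. Elsewhere the same SAP labels work as exploratory when that is meant (the durability model in 5.5.3.1 and all of 5.6), and the Part A SAP (6.5) tests its secondary efficacy endpoints in a fixed sequence. Here there is neither a label nor a sequence.

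**Working it through.** **Inputs**

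- Level per test: two-sided 0.05 (SAP for Parts B and C, 5.5.3.2).
- Superiority thresholds: lower limit above 1 (GMR) and above 0 (SRR difference), same section.
- Not given in the documents: the expected SRR, the titer SD, the within-subject correlation and the number in the pre-booster-negative immunogenicity set. These are assumed below and shown as ranges. For scale, the Part A SAP (6.7.1, Table 6) plans 6 × 150 = 900 evaluable baseline-negative mRNA-1273 participants before any Part C attrition.

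**1. The plan's own figure.** A two-sided 95% interval leaves 1 - 0.975 = 0.025 in the superiority direction, and 2 × 0.025 = 0.05. This reproduces the stated level. The critical value is 1.96.

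**2. Either-endpoint error, true GMR = 1 and true SRR difference = 0.**

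- Upper bound: 0.025 + 0.025 = 0.050.
- Independent tests: 1 - (1 - 0.025)² = 1 - 0.950625 = 0.0494, or 1.98 times 0.025.
- Correlated normal statistics: 1 - Φ₂(1.96, 1.96; ρ), where Φ₂ is the bivariate normal distribution function.

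| ρ | 0 | 0.3 | 0.5 | 0.7 | 0.9 | 1 |
|---|---|---|---|---|---|---|
| Error | 4.94% | 4.76% | 4.54% | 4.17% | 3.52% | 2.50% |

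**3. Both endpoints derived from the same titers.** This simulation used paired log-normal titers, seroresponse defined as a titer above a fixed threshold, within-subject correlation 0.3, a paired t interval for GMR and the adjusted Wald interval for the paired SRR difference. There were 20,000 runs per setting.

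| n | SRR | GMR false | SRR false | Either | Correlation of statistics |
|---|---|---|---|---|---|
| 200 | 70% | 2.44% | 2.37% | 4.01% | 0.69 |
| 200 | 90% | 2.51% | 2.21% | 4.28% | 0.52 |
| 200 | 98% | 2.55% | 0.78% | 3.22% | 0.30 |
| 200 | 99.5% | 2.44% | 0.03% | 2.46% | 0.18 |
| 600 | 70% | 2.41% | 2.26% | 3.95% | 0.70 |
| 600 | 90% | 2.19% | 2.31% | 4.08% | 0.52 |
| 600 | 98% | 2.60% | 2.32% | 4.71% | 0.30 |
| 600 | 99.5% | 2.33% | 0.52% | 2.80% | 0.17 |

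Each single-endpoint error stays at or below about 2.5%, within simulation error. Only the union exceeds it. Near the ceiling the adjusted Wald interval is conservative and the SRR test rarely rejects, so the excess almost disappears.

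**4. If GMR is truly above 1.** A GMR superiority conclusion is then correct. Only the SRR test can err, at 2.5% or less.

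**5. What reduces the error.**

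- Requiring both noninferiority tests first: no change in any simulated setting (for example 4.28% before and after), because both noninferiority tests pass almost always when the booster is truly equal.
- Fixed order, GMR then SRR: a false conclusion needs a false GMR rejection first, or a true GMR superiority followed by a false SRR rejection. The error is at most 2.5% (2.2% to 2.6% simulated at equality).
- Bonferroni split, 0.0125 one-sided each: 1 - (1 - 0.0125)² = 2.48% if independent, and at most 2.5%.

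**6. A second assay.** If MSD binding antibody is given the same table there are four tests: 1 - 0.975⁴ = 9.6% if independent, with a bound of 4 × 0.025 = 10%.

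**The case against.** The strongest reply is that the SAP makes no claim about either endpoint. Each conclusion names its own endpoint, each is made at its stated level, and the word *nominal* signals that no familywise control is claimed. This stands. A reader might infer that each superiority conclusion carries more error than the table states; the documents do not support that.

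Other stronger readings also fail:

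- **That the Part C success decision is inflated.** It is not. Both noninferiority tests must pass, and that rule needs no adjustment.
- **That the table contradicts the both-endpoints rule.** That rule governs only the noninferiority objective. If SRR fails noninferiority, the same table says so, and a GMR superiority row can stand beside it without implying that the objective is met.
- **That the missing noninferiority precondition causes the inflation.** Step 5 shows that it does not; the missing order or split does.
- **That the error is twice 2.5%.** Twice is a ceiling. Protocol 2.2.2 and 4.3 cite a booster response 1.7-fold the primary-series peak of this trial. If GMR is indeed superior here, at most 2.5% remains.
- **That Section 6 of the SAP is false.** Protocol 9.5.3.2 leaves further immunogenicity considerations to the SAP, and the added row reads the planned interval against a second threshold. Recording it there would be housekeeping.

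What survives is narrower. The table says superiority is demonstrated, on either of two endpoints, with no exploratory label and no rule for the pair.

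**Conclusion.** The point holds in a limited form. The SAP adds two formal superiority conclusions that the protocol does not plan and leaves their joint error undefined. The excess over 2.5% arises only when neither endpoint is superior, and it depends on quantities the documents do not give. Under the assumptions in step 3 the combined error runs from about 2.5% to 4.7%; step 2 gives the general range and the 5% ceiling. These figures are for one assay and one analysis method per endpoint. Testing a second assay formally would raise the ceiling.

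This is a cheap improvement to secondary endpoints in an open-label part of the study. It does not cast doubt on the noninferiority conclusion.

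**What to change.** Add to 5.5.3.2 a statement to this effect: *Superiority will be tested on PsVNA titers in fixed order, GMR first and SRR only if GMR superiority is shown, each at two-sided 0.05. Results for MSD binding antibody are descriptive.* The ordering is what controls the error. Also requiring both noninferiority tests to pass first would align the superiority claim with the Part C objective, but does not lower the error.

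Alternatively, reword row 3 of each table as a descriptive statement that the lower limit exceeds 1 (GMR) or 0 (SRR difference).

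The cost is a short statement or two table cells. Estimates, analysis sets, intervals and noninferiority criteria stay as they are. The downside is small: under the fixed order, SRR superiority cannot be claimed unless GMR superiority is shown, and MSD results carry no formal superiority claim.
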